5.2 Statistical analysis

A single statistical analysis will be performed at the end of the study. An intention to treat (ITT) approach will followed, i.e. statistical analysis of safety will be based on data from all patients and from whom meaningful data were collected. Data will be displayed graphically for visual inspection. Descriptive statistics will be presented as means, SEM and ninety percent confidence levels of the means.

Baseline characteristics. The subject disposition will be summarized. Protocol violations will be listed per subject, describing the nature of the violation. Subjects failing to complete the study (as well as the times and reasons for discontinuation) will be displayed. The demographic, background and baseline data will be presented descriptively.

Analysis of Safety. Adverse Events, as reported throughout the course of the trial will be listed individually, per treatment group. Pre-, study and post-study findings of **physical examination, vital sign variables, laboratory variables** (haematology, clinical chemistry and urinalysis), and 12-lead ECG if needed will be listed individually and summarized; values outside the normal range will be listed.

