ENDPOINTS:	
EFFICACY
 
 1. Behavioral improvement with the validated scales for autistic spectrum disorders 2. Examination by child psychologist 
SAFETY
 
 1. Adverse events, especially frequency and intensity of agitation episodes 2. Modification of vital signs: blood pressure, heart rate, respiratory rate, body temperature. 3. Modification of laboratory tests: Haematology: RBC, MCHC, MCH, MCV, RDW, Hct, Hb, WBC Differential count –lymphocytes monocytes, neutrophils, eosinophils, basophils; CD45+; blood cultures Biochemistry: Serum - Bilirubin (total) AST, ALT, LDH, glucose, urea, creatinine, sodium, potassium, chloride, calcium., MB microbiology; IP – Inflammatory panel
SAMPLE SIZE:	at least 25 patients, optimum 40 patients enrolled
STATISTICAL ANALYSIS:	Summary statistics will describe the safety variables. Significance testing will be done using analysis of variance for continuous and chi-square test for categorical variables. ($\alpha = 0,05$)

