2 STUDY OBJECTIVES

The primary objective of this study is to investigate the comparative efficacy of the UCB infusion and the non-invasive treatments for improving the functioning of children with ASD.

A secondary objective is to determine whether there are significant differences in the safety profiles of the two treatments administered

In addition there will be an evaluation of the structural changes in the CNS of the children with ASD, done by MRI

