3 STUDY PLAN AND PROCEDURES

3.1 Study design

This is a twelve months long, open-label, crossover study to evaluate the comparative efficacy and safety of UCB versus non-invasive treatments in children with ASD. Each participant will receive both treatments in a random sequence.

The UCB is autologous, previously harvested at the child's birth and cryopreserved in liquid nitrogen for later use.

The UCB infusion was performed at Angiomedica Hospital, [name] as main site and in two additional clinical sites: Medicover Hospital, [name], and Ponderas Academic Hospital, [name], all in Bucharest, Romania by anesthesiologist and pediatric physician, based on the Duke protocol.

Prior to UCB infusion, HLA typing of the child will be performed at the National Institute of Hematology, as well as the HLA typing of the UCB prior to thawing – for positive identification. During this time the UCB collection will be kept in liquid nitrogen for a maximum of 72 hours, after which thawing and preparing of the UCB for infusion will be performed by [name]; the thawing is done in optimal conditions for preserving simultaneously both sterility and viability of the cryogenated cells - the Vita 34 or Rubinstein protocols; testing for viability will be done with Trypan Blue and flowcytometry. Choosing optimal conditions is based upon the minimum number of processing steps necessary (fewest number of centrifugations and shortest time of processing, with best recovery of various stem cells) and ensuring sterility.

The non-invasive treatment combination is prescribed by the study investigator after the three questionnaires are answered and an evaluation by child therapist/psychologist is performed independently. This treatment is

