4 STUDY MEASUREMENTS AND ENDPOINTS

In this study the following endpoints will be measured/recorded

1. Efficacy - difference in the scores on the questionnaires M-CHAT, Q-CHAT and CAST before and after each treatment

2. Safety – type, severity, duration, treatment and amelioration of each of the adverse effects occurring during respective treatments.

4.1 Primary Safety Endpoints.

–

1. Adverse events (type and frequency)
2. Physical examination parameters (body mass, height, etc)
3. Vital signs: blood pressure, heart rate, respiratory rate, body temperature
4. Laboratory tests
 - HLA testing by genetic sequencing
 - Haematology: CBC - RBC, HB, MCHC, MCH, MCV, RDW, Hct, Hb, WBC Differential count –lymphocytes monocytes, neutrophils, eosinophils, basophils, flowcytometry - CD34+, TNC, viability %
 - Microbiology – presence and sensitivity of pathogens
 - LFTs Serum - Bilirubin (total and conjugated) AST, ALT, GGT, LDH, glucose
 - IP – serum protein electrophoresis, ESR, CRP, fibrinogen
 - Els - sodium, potassium, chloride, calcium, magnesium.

4.2 Measurements at each visit.

See section 3.1.1 for the visit schedule.

Visit 0: Screening Visit

Patients will be examined within 14 days prior to the first ingestion of the investigational products to assess their eligibility to participate. For each child both parents will consent in writing (Appendix 1, Informed Consent Form) to the screening process before the start of the examination. The consent form will also include the study information leaflet.

The examinations and investigations will include:

- Medical history, including history of past use of medications, demographics (date of birth, sex, race) and ASD diagnosis.
- Physical examination including assessment of general appearance, cardiovascular, lungs, mouth, throat and abdomen and measurement of height and body weight. The examination will be made in accordance with the normal clinical routines at the trial center.
- Vital signs: systolic and diastolic blood pressure in supine (after 5 minutes rest) and standing positions (1minute), pulse, respiratory rate and oral temperature.
- Laboratory tests: HLA, Haematology, (see section 4.4.3.2); baseline plasma levels of IP, Els, LFTs (these can be drawn also at V1 if considered by the study PI)

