5 STATISTICAL METHODS

5.1 Determination of sample size

Based on literature we expect that a sample size of minimum 25 participants will be needed in order to observe an alpha value of 0.05 (95% probability) with a p value of 0.05 and a power of 80%. ANOVA testing will be performed on the respective groups of patients

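### Section 5.2 plans 90% limits of means although the tests run at alpha 0.05, and no estimate or interval is planned for the UCB versus non-invasive difference

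*Combined protocol and SAP*

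**What the plan says.** On presentation, Section 5.2 gives one general rule, placed before its paragraphs on baseline characteristics and safety: "Descriptive statistics will be presented as means, SEM and ninety percent confidence levels of the means". There is no matching paragraph for efficacy.

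On the level, the Statistical Analysis row of the synopsis states "Significance testing will be done using analysis of variance for continuous and chi-square test for categorical variables", with alpha 0.05. Section 5.1 bases the sample size on the need "to observe an alpha value of 0.05 (95% probability) with a p value of 0.05 and a power of 80" per cent, and names ANOVA again. Neither place states sidedness.

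On the question, Section 2 says "The primary objective of this study is to investigate the comparative efficacy of the UCB infusion and the non-invasive treatments". Section 4 defines efficacy as the "difference in the scores on the questionnaires M-CHAT, Q-CHAT and CAST before and after each treatment". Section 3.1 adds "Each participant will receive both treatments in a random sequence", so the comparison is made within each child.

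No section plans a point estimate or a confidence interval for the difference between the two treatments.

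**The concern.** There are two mismatches.

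- **Level.** The tests use 0.05, which the plan itself glosses as 95%, but the limits are at 90%. A 90% interval can be justified, for example by an equivalence or one-sided aim, but the plan has neither and gives no other reason. If the means include mean change scores, a result with p between 0.05 and 0.10 would have an interval that excludes zero beside a test that does not reject.
- **Quantity.** The trial asks how the two treatments compare within a child. Limits around single means do not answer that. If the plan is followed literally, the primary comparison could be reported as a p-value alone, with no estimate of its size or precision.

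The use of SEM adds a smaller problem. It describes the precision of a mean, whereas a descriptive table should show the spread between children.

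**Working it through.** **Inputs from the documents.** Alpha 0.05 (synopsis, Section 5.1); 90% limits of the means (Section 5.2); at least 25 children, optimum 40 (synopsis); change before to after each treatment (Section 4); questionnaires at V0, V2 and V3 (Section 3.1.1). **Assumptions.** Two-sided tests; equal SDs of the two change scores; no adjustment for period; the correlation *r* between a child's two change scores, which the documents do not give.

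**The plan's own figure.** Section 5.1 says "Based on literature we expect that a sample size of minimum 25 participants will be needed", but gives no effect size, SD or correlation, so 25 cannot be reproduced. Back-solving for 80% power at two-sided 0.05 with 25 within-child differences gives a standardised difference of (1.960 + 0.842)/√25 = 0.56 (normal approximation), or 0.58 with the t distribution. Nothing below depends on this.

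**1. 90% against 95% limits.** The half-width is t × SD/√n, so the ratio is t(0.95, n−1)/t(0.975, n−1).

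| n | t for 90% | t for 95% | 90% ÷ 95% | 95% wider by |
|---|---|---|---|---|
| 25 | 1.711 | 2.064 | 0.829 | 20.6% |
| 40 | 1.685 | 2.023 | 0.833 | 20.0% |

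For a single mean change, exclusion of zero by the 90% interval is the same as two-sided p < 0.10.

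**2. Single means against the contrast.** SE(difference) = SD × √(2(1−r)/n). Treating the two means as independent gives SD × √(2/n). The ratio, independent over correct, is 1/√(1−r).

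**3. What *r* might be.** V2 closes the first period and opens the second. If the changes are V2−V0 and V3−V2, V2 enters them with opposite signs.
- Equal variances and the same correlation ρ between all visits: covariance = −(1−ρ)σ², each variance = 2(1−ρ)σ², so *r* = −0.5 whatever ρ is. Ratio = 1/√1.5 = 0.82.
- Correlation decaying with time (AR(1), visits treated as equally spaced): *r* = −(1−ρ)/2. At ρ = 0.5, *r* = −0.25 and the ratio is 1/√1.25 = 0.89.
- Child-specific trends could move *r* upward. At *r* = +0.5 the ratio would be 1/√0.5 = 1.41.

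So the separate means could make the contrast look either more or less precise than it is.

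**4. What the planned display would show at n = 25** (t with 24 df, in SDs of the change score). The planned 90% half-width of one mean is 1.711/5 = 0.34 SD whatever *r* is. The last column is the two-sided level of judging a difference by whether the two 90% intervals fail to overlap.

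| r | 95% half-width of the difference | Level of the non-overlap rule |
|---|---|---|
| −0.5 | 2.064 × √3/5 = 0.71 | 0.060 |
| −0.25 | 2.064 × √2.5/5 = 0.65 | 0.041 |
| 0 | 2.064 × √2/5 = 0.58 | 0.023 |
| +0.5 | 2.064 × 1/5 = 0.41 | 0.002 |

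The width the reader needs changes with *r*, and the planned display does not.

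**The case against.** The strongest reply is that the sentence concerns descriptive statistics. Testing is specified separately at 0.05, no decision rule uses the 90% limits, and an interval labelled 90% has the coverage it claims. All of that stands: the type I error of the planned tests is unchanged.

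It can also be said that the rule may be meant only for safety and baseline summaries. The intention-to-treat sentence beside it is about safety, the paragraphs that follow cover baseline and safety, and the synopsis attaches summary statistics to the safety variables. This is a fair reading. On it, though, the plan says nothing at all about how efficacy estimates will be shown, so the gap on the treatment difference remains.

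SEM is partly a matter of presentation, since SD = SEM × √n (5 × SEM at n = 25).

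Two stronger readings are tempting, and the documents support neither.
- A reader might infer that the 90% limits put the treatment comparison at a 10% error rate. The 10% applies to a single mean change against zero. The limits are not for the difference, and a non-overlap rule has a different level that varies with *r*.
- A reader might infer that separate intervals must overstate the standard error of the difference, by 1.4 to 3.2 times, by taking correlations of 0.5 to 0.9. No correlation is given, and because the two changes share V2 with opposite sign, the error may run the other way.

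**Conclusion.** The point holds as a reporting inconsistency joined to a gap in estimation. The 90% level is unexplained and does not match alpha 0.05: the half-widths are 83% of the 95% ones at 25 or 40 children. More importantly, no estimate or interval is planned for the comparison that is the primary objective, and moving the existing limits to 95% would not supply one.

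The interval ratio rests only on the stated levels and sample sizes, with t-based limits. The remark about p < 0.10 assumes two-sided tests and that the means include mean changes. The direction and size of any misstatement of precision for the contrast cannot be settled from the documents. The negative values of *r* assume that change runs from V0 to V2 and from V2 to V3, with the visit correlations stated in the working.

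This is worth correcting because the correction is cheap. It is not a flaw in the validity of the tests.

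**What to change.** Replace the sentence in Section 5.2 with wording to this effect: *Results will be presented as mean and SD by treatment and visit. For each questionnaire, the within-child difference in change score (UCB minus non-invasive) will be presented with its 95% confidence interval from the crossover ANOVA used for the test. Any other confidence intervals will be at 95%.*

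For this to work, the ANOVA named in the synopsis and Section 5.1 must be written out as a crossover model, with the visits that define before and after each treatment, so that the interval and the test come from the same fit.

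The cost is intervals about 20% wider than the planned 90% ones and a little more analysis work. No further data, visits or children are needed.

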Final Protocol:	June 2019	Clean File:	June 2019
Ethics Approval:	January 2019	Statistical analysis:	
Clinical Phase:		Study Report:	
OBJECTIVES:	To compare the safety and efficacy of administering intravenous autologous cord blood versus personalized noninvasive treatments to children with developmental disorders of the autistic spectrum		
STUDY DESIGN:	An open-label, pilot crossover study over a 12-month period. Participants will be screened and randomized at Visit 0 and at visit V1 will be receiving either intravenous umbilical cord blood or noninvasive treatment. At V2, at 2 months after V1, the other treatment is administered and subsequently the child will be evaluated by questionnaires and child therapist. Parents will report adverse events and complete the M-CHAT, Q-CHAT and CAST questionnaires. Modifications on these questionnaires will be analyzed statistically as a quantitative measure of child's improvement.		
SUBJECTS:	
Inclusion criteria Males and females between 3 and 7 years of age:
 
 • parents informed of the nature of the study and will give written informed consent, • have body weights between 10-30 kg, • have no clinically significant abnormal values on hemoleucogram during screening, • be on no regular medical treatment • have no known allergies to treatments 
Exclusion criteria
 
 • Any genetic or metabolic disease or condition which might compromise the haematopoietic, renal, endocrine, pulmonary, central nervous, cardiovascular, immunological, dermatological, gastrointestinal or any other body system. • History of allergic conditions – asthma, urticaria, eczema. • History of autoimmune disorders 		

	
 • Intake of any medication within 14 days before start of the study • Presence of significant abnormal hemoleucogram results during screening.
TREATMENT TO BE EVALUATED	
Active Treatment A: Autologous umbilical cord blood administered intravenously as single treatment .
 
Active Treatment B: Personalized daily treatment following evaluation with a combination of intranasal Oxytocin; Curcumin; Lecithin, Piracetam, Tecfidera; PQQ; Magnesium citrate and vitamin B6

DURATION OF STUDY	12 months

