3.1.1 Scheduled study visits

Recruitment of patients will occur during initial contacts with the study coordinator [name] who will present the parents with the opportunity to enroll in the study, and when general information will be given about the study on timeline, procedures involved, tests, costs.

After agreeing in principle to participate in the study, parents and child will be scheduled for **Visit 0**, at which the patients' blood is drawn for testing, questionnaires are completed, the patient is evaluated by the child therapist and is randomized for receiving treatment A (UCB infusion) or B (noninvasive treatment), and the necessary arrangements are made for UCB release from the respective banking site.

Visit 1 is scheduled within 7-14 days from V0, and during this study visit the child will receive either treatment A or B. Treatment B (noninvasive) is administered daily for 6 weeks, and is followed by 2 weeks with no treatment (washout period)

Visit 2 follows at 8 weeks distance from V1, which includes the 2 week washout period after the first treatment is administered. New blood tests are performed, also questionnaires and evaluation by child therapist, and the other treatment in sequence is administered.

Visit 3, Visit 4, and Visit 5 are scheduled at 16, 24 and 52 weeks after first treatment was administered (V1) and involve the neuropsychological evaluation of the child by the therapist and with the 3 questionnaires; brain imaging is recommended at 52 weeks

	Visit 0	V1	V2 (+ 8 weeks)	V3 (+16 wks)	V4 (+24 wks)	V5 (+52 wks)
Labs	CBC, LFTs, Els, HLA; IP	HLA MB	CBC, LFTs, Els, HLA; IP; MB			
Imagis-tics	MRI/CT					MRI/CT
Neuro/Psi Evaluation	M-CHAT-R; Q-CHAT; CAST; - Child therapist	x	M-CHAT-R; Q-CHAT; CAST; - Child therapist	M-CHAT-R; Q-CHAT; CAST; - Child therapist	M-CHAT-R; Q-CHAT; CAST; - Child therapist	M-CHAT-R; Q-CHAT; CAST; - Child therapist
Treatment started	randomi-zation	A/B	B/A	X	X	X

CBC – complete blood count with differential; LFTs – liver function tests, Els – electrolytes; IP – Inflammatory panel – ex ESR, CRP, serum protein electrophoresis, neopterin, IL-6; HLA – Typing of patient HLA- A, HLA-B, HLA-DR; MB - microbiology

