3.3 Investigational Products and Treatments

3.3.1 Treatment Schedule

Each treatment arm is administered and considered active for a period of maximum 8 weeks; the non-invasive treatment is administered for 6 weeks followed by a 2-week “wash-out” period, and the UCB infusion will be followed by supplement administration after an 8-week interval. Patient evaluation, registration informed consent and randomization occur at initial visit 0 (V0); followed after 14-21 days by V1 (longer for the preparation of UCB infusion), during which the first treatment is administered; V2 after another 8 weeks, at which the second treatment is administered, and V3, V4, and V5, at 16, 24 and 52 weeks respectively after V1.

A tabulated summary of the study visits was given above Section 3.1.1

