4.3 Specific detail on measurements

4.4.1 Adverse events

An adverse event is the development of an undesirable medical condition - e.g. symptoms or abnormal results of an investigation - or the deterioration of a pre-existing medical condition (not relevant in this study). AE's will be collected by means of a standard question: "Have you had any health problems since the previous visit?" AE's will be recorded at every visit. Spontaneously reported AE's and/or observed AE's and the subject's response to this question will be recorded on the AE form with information about seriousness, action taken, date of onset and recovery, maximum intensity and outcome. The subjects will be asked to assess the intensity of the reported Adverse Event according to the following scale:

Mild = awareness of sign or symptom, but easily tolerated
Moderate = discomfort sufficient to cause interference with normal activities
Severe = incapacitating, with inability to perform normal activities.

A Serious Adverse Event is an adverse event occurring during any phase of the study and at any dose of the investigational product or placebo, which fulfils one or more of the following criteria:

- Results in death;
- Is immediately life-threatening;
- Requires in-subject hospitalization;
- Results in persistent or significant disability or incapacity.

The causality of Serious Adverse Events (i.e. the relationship to study treatment) will be assessed by the investigators, who in completing the relevant Case Report Form must answer ‘yes’ or ‘no’ to the question “Do you consider that there is a reasonable possibility that the event may have been caused by the study medication?” The following factors should be considered when deciding if there is a “reasonable possibility” that an Adverse Event may have been caused by the investigational product.

- Time course of events and exposure to suspect drug – did the AE occur in a reasonable temporal relationship to the administration of suspect drug?
- Dechallenge experience – did the AE resolve or improve on stopping or reducing the dose of the suspect drug?
- Rechallenge experience - did the AE reoccur if the suspected drug was reintroduced after having stopped?
- Laboratory tests – has a specific laboratory investigation confirm the relationship?
- No alternative cause - the AE cannot be reasonably explained by another aetiology such as an underlying disease (not previously present), other drugs or environmental factors.

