4.4 Measurements recorded daily in a diary

A diary will be filled in at home during the entire study in the morning after taking the morning dose and at night after the evening before going to bed. The following variables will be recorded:

- i) Intake of study medication (if, time and if with food)
- ii) Occurrence of any adverse effects.
- iii) Intake of any incidental medication

The subjects will record the time (morning and evening) that the study medication has been taken. The recordings are a measurement of compliance.

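### Section 5.2 lists adverse events per treatment group for the whole trial, without defining the group in a crossover or applying the protocol's own 8-week limit, so the safety comparison is diluted or not delivered

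*Combined protocol and SAP*

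**What the plan says.** The adverse event analysis in section 5.2 is one sentence: "Adverse Events, as reported throughout the course of the trial will be listed individually, per treatment group". It contains no definition of treatment group, no rule for assigning an event to a treatment, no time window and no exposure denominator.

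Other sections bear on it:

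- **Schedule (3.1.1).** "Visit 2 follows at 8 weeks distance from V1, which includes the 2 week washout period after the first treatment is administered". Visits 3, 4 and 5 are at 16, 24 and 52 weeks after V1. Treatment B is given for 6 weeks and then stopped for 2; treatment A is a single infusion.
- **Active period (3.3.1).** "Each treatment arm is administered and considered active for a period of maximum 8 weeks".
- **Endpoint (section 4, item 2).** Safety is defined by adverse effects that occur during the treatment concerned.
- **Collection.** "AE's will be recorded at every visit" (4.4.1), with date of onset on the form. Also, "A diary will be filled in at home during the entire study" (4.4).
- **Purpose.** Section 2 makes it a secondary objective to find whether the safety profiles of the two treatments differ significantly. The synopsis names analysis of variance and chi-square tests at 0.05 by type of variable.
- **Allocation (3.3.2).** The starting treatment is random; no ratio or method is given.

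**The concern.** In a crossover every child receives both treatments, so treatment group has no obvious meaning once the second treatment has started. Events are collected to week 52, but both treatments have been started by week 8, and by week 16 both of the protocol's active periods are over. Whatever is recorded after that follows both treatments.

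Two limits already in the protocol, the 8-week active period and the endpoint restricted to the treatment concerned, would settle most of this. Section 5.2 uses neither. The comparison at stake is the trial's secondary objective, in children aged 3 to 7 years. If early events after one treatment are mixed with a long stretch of background events, a real difference is harder to see.

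**Working it through.** The documents give no adverse event rate and no safety calculation to reproduce. The schedule figures come from sections 3.1.1 and 3.3.1, and the number of children is the minimum of 25 in section 5.1. Rates, rate ratios and sequence splits below are assumptions for illustration.

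**1. Two readings of treatment group.**

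- *Most recent treatment.* First treatment: V1 to V2 = 8 weeks. Second treatment: 52 − 8 = 44 weeks. Time beyond the two active periods: 52 − 8 − 8 = 36 weeks, which is 36/52 = 69% of the trial and 36/44 = 82% of the second period. A child who receives B second takes it for 6 of the 44 weeks counted to it (14%).
- *Sequence.* Each group has 52 weeks per child, and no event is attributed to A or B.

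Steps 2 to 4 use the first reading.

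**2. Dilution with equal sequences.** Let the weekly background rate be constant and equal, and let the rate be multiplied by R in the 8 weeks after A. Average time per child and treatment is (8 + 44)/2 = 26 weeks, of which 8 are active and 18 are not. The apparent ratio is (8R + 18)/26.

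| True ratio R | Apparent ratio, whole trial | Ratio on 8-week windows |
|---|---|---|
| 1.5 | 30/26 = 1.15 | 1.5 |
| 2 | 34/26 = 1.31 | 2 |
| 3 | 42/26 = 1.62 | 3 |

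**3. Cost in power.** Take the share of children with at least one event, 25 per treatment, two-sided 0.05, pairing ignored, and R = 3. For weekly background rates of 0.01, 0.02 and 0.05, power is 27%, 46% and 76% with the 8-week window, against 15%, 23% and 39% with the whole trial.

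**4. Unequal sequences with no true difference.** Child-weeks labelled A = (A-first × 8) + (B-first × 44), and the reverse for B.

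- 10 A-first, 15 B-first: A = 80 + 660 = 740, B = 120 + 440 = 560. Count ratio 740/560 = 1.32.
- 15 A-first, 10 B-first: the reverse, 560/740 = 0.76.
- Probability of a split at least this uneven, in either direction, under simple 1:1 randomisation of 25: 2 × P(Bin(25, 0.5) ≤ 10) = 0.42.

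Dividing by child-weeks removes this imbalance but not the dilution in step 2.

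**5. Late events after A.** If events related to A arose evenly over 12, 16 or 26 weeks after the infusion, the share falling after V2 in A-first children, and so labelled B, would be 1 − 8/12 = 33%, 1 − 8/16 = 50% or 1 − 8/26 = 69%.

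**The case against.** The strongest reply is that section 5.2 plans an individual listing. With onset dates recorded, a listing loses nothing and can later be cut by any window. The endpoint definition in section 4 already implies a limit to the treatment period. For serious events, section 4.4.1 adds a causality judgement that considers time course and dechallenge.

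Much of this is fair, and it rules out several stronger readings:

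- A reader might infer that the plan assigns every event to week 52 to a treatment, 8 weeks against 44. The text does not say so; that is one reading of an undefined term.
- A reader might infer a planned chi-square test on whole-trial events. The synopsis names the test only generically, for categorical variables, and nothing specifies it for these counts.
- A reader might take 8 against 44 as a bias between A and B. It is a difference between periods. With equal sequences and no dropout, each treatment totals 25 × 26 = 650 child-weeks.
- A 12/13 split with a true doubling gives (668 + 200)/632 = 1.37, but that figure mixes dilution with an exposure imbalance of 668/632 = 1.06. The clean dilution figure is 1.31.

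What does not stand is that the listing is enough. It is the only adverse event analysis that section 5.2 specifies, while section 2 calls for a comparison. The causality question covers serious events only and does not ask which of the two treatments is suspected. The limits in sections 3.3.1 and 4 exist, but section 5.2 does not carry them forward.

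**Conclusion.** The point holds as a failure to define the treatment label and to reconcile section 5.2 with sections 3.3.1 and 4. No assumption is needed for the schedule: 8 weeks after the first treatment, 44 after the second, and 69% of the trial outside any active period. Under one reading of treatment group the comparison is diluted; under the other it is not made.

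The size of the dilution (a doubling seen as 1.31) is illustrative. It rests on a constant background rate, equal sequences and an excess confined to 8 weeks. A difference in counts where none exists needs unequal sequences, and it can go either way (1.32 or 0.76 at 10/15 or 15/10). The 0.42 covers both directions and assumes simple 1:1 randomisation, which the protocol does not state. The documents do not support a claim that the plan favours one treatment.

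This should be corrected before analysis. It concerns the secondary objective and does not touch the efficacy analysis.

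**What to change.** Reconcile section 5.2 with sections 3.3.1 and 4:

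1. Define the treatment label of each event by its onset date.
2. Make the between-treatment comparison on the equal 8-week windows V1-V2 and V2-V3. Report by treatment, period and sequence: children affected, and events per child-week.
3. Use a within-child (paired) comparison, since each child contributes both windows.
4. List events after week 16 separately by sequence, attributed to neither treatment alone.

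The cost is SAP wording and table shells. Onset dates and the daily diary are already planned, so no new data are needed.

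There is a downside. Section 3.3.1 states the 8 weeks as part of the treatment schedule, not as a safety risk window, and late effects of the first treatment can still fall in the second window. In the 26-week illustration, 8/26 = 31% of A-related events in A-first children would still fall in B's window, and 10/26 = 38% would move to the separate listing. The results by sequence and period should therefore be shown, and this limitation stated.
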